## Study Objectives

Rise for Health will examine 3-month changes in biomarkers of healthy aging and physical, emotional, and cognitive functioning across a 3-arm randomized trial: (1) healthy living attention control (Healthy Living), (2) reduce sitting time (Reduce Sitting), and (3) increase sit-to-stand transitions (Increase Transitions). The study aims to enroll 405 postmenopausal women into the 3-month trial. The primary aim is to compare changes in glucoregulatory biomarkers (fasting plasma insulin and glucose, HbA1c, and HOMA-IR) and blood pressure over 3 months for the 2 intervention arms compared with the attention control condition. We hypothesize that, compared with those allocated to the attention control arm, participants in the 2 intervention arms will have greater improvements in glycemic control and blood pressure. In addition, we will evaluate the dose-response effects of sitting behavior changes on glucoregulatory biomarkers and blood pressure. We hypothesize that greater improvements in the target behavior will be associated with greater improvements in glucoregulatory biomarkers and blood pressure. The secondary aims of the study are to examine the effects of the intervention on physical, emotional, and cognitive functioning. This project will also explore (1) the modifying effects of age on the relationship between the 3 conditions and primary and secondary outcomes, (2) the psychosocial and mediators and moderators of changes in sitting behaviors, and (3) the differences in outcomes between the 2 sitting interruption intervention arms. The purpose of this paper is to describe the study protocol of Rise for Health, a 3-arm randomized trial, to assess ways of interrupting sitting in postmenopausal women.

The institutional review board of the University California San Diego (UC San Diego) approved all study procedures, and all participants will provide written informed consent. Study recruitment, participant safety, and progress are reviewed semiannually by an external independent data safety monitoring board appointed by the National Institutes of Health (NIH).

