## **Baseline Visit**

Participants return to the clinic after at least seven days of wearing the two devices. Data from activPAL are screened for sitting time (more than 7 hours on a majority of measured days) and sit-to-stand transitions (70 or fewer transitions per day on a majority of measured days) to confirm eligibility. Participants provide fasting blood samples via a finger prick to screen for HbA1c. Those who pass these final eligibility criteria then have a venous blood draw taken by a certified phlebotomist and complete additional questionnaires. Participants receive a total of US \$35 for completing baseline measures. After all baseline assessments are complete, the participants are then randomized.

Randomization is stratified by BMI (overweight vs obese) and employment status (full-time vs nonfull-time employment). A computerized randomization scheme was created using the STAR program grant Biostatistics Core, using a random number generator. A stratified permuted block design is used in this study. After randomization, the participants review the expectations and requirements of their study group assignment (details given in the *3-Month Intervention* section). Data collectors and the principal investigator are blinded to the study group assignment.

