Sedentary Behavior Interrupted:
A Randomized Trial of 3-Month Effects on
Biomarkers of Healthy Aging and Physical
Functioning in the Real World (P2)

NCT03473145

August 26, 2025

Statistical Plan

Baseline characteristics were compared across the 3 treatment arms using ANOVA for continuous variables and χ^2 or Fisher exact tests for categorical variables. Study-related adverse events were tabulated by group using a standard medical dictionary for regulatory activities body system categories.

The primary analysis comparing the sit less and sit-to-stand interventions with the healthy living controls used the intent-to-treat principle. Linear mixed models (LMMs) were applied, allowing for the inclusion of partially complete records, thereby reducing complete case analysis biases. The model included baseline and 3-month outcomes as dependent variable; time (baseline, 3-month), group (active, control), and the group*time interaction were fixed-effect independent (categorical) variables. A subject-specific (random) intercept was included to model individual heterogeneity in outcomes. A significant group*time interaction indicated that outcome changes differed between that intervention and the control arm; this difference of outcome changes between intervention and control arms represents the intervention effect.

To reduce the chance of false positives, we first fit the aforementioned LMMs for 2 primary composite outcomes: (1) glucoregulatory outcomes defined as the average of 4 Z scores of insulin, glucose, HbA1c, and HOMA2-IR; and (2) blood pressure composite defined as the average of 2 Z scores of systolic and diastolic blood pressure. The Z score for each participant for a specific marker and time point was derived by subtracting the sample baseline mean from the participant's marker value at that time point and dividing this difference by the sample baseline SD. This composite score analysis represents an omnibus test of intervention efficacy across multiple (correlated) outcomes: rejection of the null hypothesis would suggest that the intervention (compared with controls) effected changes across components of the composite score. After this composite score analysis, we compared group differences for each of the outcomes; we present intervention results for the individual markers.

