Several secondary analyses were conducted. First, we evaluated intervention effects adjusted for baseline stratification variables (obesity status, employment status). Second, we evaluated group differences in outcomes between the 2 intervention arms. Third, we evaluated changes in physical activity (standing, stepping, light physical activity, and MVPA) by intervention arm. Fourth, we included an indicator variable for COVID-19 (yes or no) and evaluated 3-way COVID-19*group*time interaction (by likelihood ratio tests) to test whether changes in outcomes differed between participants with delayed 3-month assessment because of COVID-19 and those who received the original protocol. Fifth, we explored whether baseline hypertension status was an effect modifier for blood pressure and whether baseline glycemic status (HbA1c < or \geq 5.7%) was an effect modifier for glucoregulatory outcomes. We also excluded participants who self-reported having type 2 diabetes at baseline and repeated the LMM analysis. Last, we examined whether changes in MVPA altered the intervention effect estimates by including MVPA at baseline and 3 months as a time-varying covariate, and the MVPA*group interaction in the LMMs.

Gaussian link functions were used in the mixed models, and diagnostic plots were generated to evaluate model assumptions. Insulin, glucose, and HOMA2-IR were log-transformed to better approximate Gaussian distributions, and results were presented as geometric means with 95% CIs derived from model estimates (β coefficients) at baseline and at 3 months, along with mean (95% CI) within group changes. For the other outcomes, sedentary behavior measures, and blood pressure, mean (95% CI) at baseline and 3 months, as well as mean (95% CI) within-group change derived from model parameters (β coefficients), are presented. Treatment effects were calculated as the mean (95% CI) of the difference (compared with the control group) in absolute changes (for all outcomes) and percent changes (for log-transformed outcomes) from baseline to 3 months.

Analyses were implemented in the R statistical programming language, and LMMs were executed by R package nlme. All hypothesis tests were 2-sided. We used significance level $\alpha=0.025$ for the primary analyses to adjust for multiple comparisons (2 intervention groups versus control). No multiple comparison adjustment was made for secondary analyses.

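### The primary mixed model leaves baseline means free in each arm, so it tests a change-score contrast; this is valid but less precise than a baseline-adjusted analysis

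*SAP*

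**What the plan says.** The Statistical Plan in the SAP puts both visits in the outcome vector and specifies that "time (baseline, 3-month), group (active, control), and the group*time interaction were fixed-effect independent (categorical) variables". For the covariance: "A subject-specific (random) intercept was included to model individual heterogeneity in outcomes". The effect is then defined: "this difference of outcome changes between intervention and control arms represents the intervention effect". The later reporting paragraph does the same, presenting treatment effects as differences from control in absolute or percent change. One stated reason for a mixed model is "allowing for the inclusion of partially complete records, thereby reducing complete case analysis biases".

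The Protocol (Baseline Visit) fixes the order of events: "After all baseline assessments are complete, the participants are then randomized".

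The primary tests are two-sided at 0.025 for each intervention against control. They are applied to two composites (glucoregulatory and blood pressure), so there are four tests.

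The secondary analyses adjust for obesity and employment status, repeat the model without participants with type 2 diabetes, and add moderate-to-vigorous activity as a time-varying covariate. They also examine subgroups: "we explored whether baseline hypertension status was an effect modifier for blood pressure", and likewise HbA1c category for the glucoregulatory outcomes. None of these adjusts the primary effect for the baseline value of the outcome itself.

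**The concern.** Because baseline is measured before allocation, any difference between arms at baseline is chance. A model with a free baseline mean in each arm does not use that fact. It subtracts the whole chance difference from the 3-month difference, when only part of it is expected to persist.

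Let ρ be the baseline to 3-month correlation, k the ratio of the 3-month SD to the baseline SD, and Δ the chance baseline difference. The part expected at 3 months is ρkΔ. The planned contrast removes Δ, which leaves an error of −(1 − ρk)Δ. This over-corrects when ρk is below 1 and under-corrects when it is above 1. The error averages to zero over randomizations, so there is no bias, but it adds variance to every confirmatory test.

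**Working it through.** **Inputs.** From the documents: the model terms and definition of effect (SAP), two-sided alpha 0.025 (SAP), and total enrolment (Protocol, Study Objectives: "The study aims to enroll 405 postmenopausal women into the 3-month trial"). Assumed: 405/3 = 135 per arm, since the allocation ratio is not stated; ρ from 0.5 to 0.9; k from 0.8 to 1.2; a fraction m of 3-month values missing completely at random; and a 0.25 SD effect for illustrating power. The documents give no power calculation, so there is no planned figure to reproduce.

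**Step 1: what the planned model estimates.** On one simulated complete data set (135 per arm, ρ = 0.7), the group-by-time estimate and the raw difference in mean change were both 0.067404. Adding 0.30 to one arm's baseline values only moved the estimate to −0.2326, a shift of exactly −0.30. The baseline weight is therefore 1. The wording of the group factor does not settle whether one three-arm model or two pairwise models were fitted, but baseline means are free in both.

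**Step 2: variances.** In baseline-SD units, with n per arm:

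- planned: (2/n)[k²(1 − ρ²)/(1 − m) + (1 − ρk)²]
- baseline-adjusted: (2/n) k²(1 − ρ²)/(1 − m)

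The planned form assumes the fitted covariance is correct. For a random intercept that holds at k = 1, and for the estimate at any k when m = 0. The avoidable part is (2/n)(1 − ρk)², which is zero only if ρk = 1.

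With k = 1 and m = 0, the planned bracket is (1 − ρ²) + (1 − ρ)² = 2(1 − ρ), so the variance ratio is (1 − ρ²)/[2(1 − ρ)] = (1 + ρ)/2.

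**Step 3: numbers at k = 1.** The detectable effect is (2.241 + 0.842) × √variance, for 80% power at alpha 0.025. Arrows run from planned to adjusted.

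| ρ | Variance ratio, complete | 10% missing | 20% missing | Detectable effect (SD), complete | Power at 0.25 SD, complete | Power at 0.25 SD, 20% missing |
|---|---|---|---|---|---|---|
| 0.5 | 0.75 | 0.77 | 0.79 | 0.375 → 0.325 | 43% → 55% | 36% → 45% |
| 0.7 | 0.85 | 0.86 | 0.88 | 0.291 → 0.268 | 66% → 74% | 57% → 63% |
| 0.9 | 0.95 | 0.955 | 0.96 | 0.168 → 0.164 | 99% → 99% | 97% → 98% |

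Example, ρ = 0.7 with 20% missing: planned (2/135)(0.51/0.8 + 0.09) = 0.01078; adjusted (2/135)(0.51/0.8) = 0.00944; ratio 0.876. The equivalent gain in participants is 1/ratio − 1: 33%, 18% and 5% with complete data, and 27%, 14% and 4% with 20% missing.

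**Step 4: unequal SDs, complete data.** The ratio is k²(1 − ρ²)/(1 + k² − 2ρk). For ρ from 0.5 to 0.9 it is 0.67 to 0.81 at k = 0.9, 0.82 to 1.00 at k = 1.1, and 0.87 to 1.00 at k = 1.2. Where ρk is near 1 there is nothing to gain.

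**Step 5: simulation.** In 20,000 simulated complete trials of 3 × 135, the variance ratios at ρ = 0.5, 0.7 and 0.9 were 0.749, 0.858 and 0.954 for k = 1; 0.816, 0.921 and 1.003 for k = 1.1; and 0.872, 0.965 and 0.980 for k = 1.2. These agree with the formulas.

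**Step 6: cost of adjusting.** Estimating the slope multiplies the variance by about 1 + 1/(405 − 5) = 1.0025. The worst case is therefore a loss of about 0.25%.

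**Step 7: does the stratification-adjusted analysis recover the loss?** On simulated complete data, adding a stratum main effect left the estimate (0.3617) and its standard error (0.0893) unchanged, because a term constant over time cancels from the change. A main-effects adjustment therefore does not help.

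**The case against.** The strongest reply is that nothing is invalid. The stated aim is to compare changes, the planned model does that, it keeps partial records, and it yields the arm-specific baseline means and within-group changes that the SAP reports. All of this is true, and the point is about efficiency only.

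Second, the size of the gain is unknown. The more striking figures use k = 1 and low ρ. The composites average four and two Z scores, which may raise ρ. The remote blood pressure measurement described under COVID-19 Considerations may add noise at 3 months alone, which shrinks the proportional loss. This stands: the gain could be negligible. It does not remove the asymmetry between a possible gain of up to 25% of variance at ρ = 0.5, k = 1 and a worst-case loss of about 0.25%.

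Third, the SAP is in the past tense. If results are known, the confirmatory tests cannot be replaced and the power gains are no longer available to them. This also stands, and it limits the remedy.

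Fourth, a careless fix could do harm. Dropping the group term while keeping only a random intercept forces equal visit variances. With complete data, the model variance is then (1 + k²)/(2k²) times the true one. The type I error is 0.018, 0.025, 0.032 and 0.039 at k = 0.9, 1, 1.1 and 1.2, against a nominal 0.025. At ρ = 0.9 the true variance can also exceed the planned one, by a factor of 1.04 at k = 1.1 and 1.11 at k = 1.2. This is a good reason to specify the covariance, but not a reason to leave the baseline unadjusted.

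**Conclusion.** The concern holds as a loss of precision, not as bias or a type I error problem. The planned contrast gives baseline a weight of 1, and no listed analysis corrects that. With equal SDs, the avoidable share of the variance is 25%, 15% and 5% at ρ = 0.5, 0.7 and 0.9 with complete data, and somewhat less with missing 3-month values. It is material at low to moderate ρ and negligible when ρk is near 1. These sizes rest on assumed ρ, k and dropout, and the power figures also rest on 135 per arm and an arbitrary 0.25 SD effect. The change is cheap and should be made, but the trial's conclusions do not become unsound without it.

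**What to change.** For each outcome, fit one model with a three-level arm factor and a common baseline mean: a time effect plus an arm-by-time term for each intervention at 3 months, with no arm main effect. Use an unstructured 2 × 2 covariance (in nlme, gls with corSymm within participant and varIdent by visit), not a random intercept alone. Test each intervention against control at 0.025, as now. This keeps participants with only a baseline value. ANCOVA of the 3-month value on baseline is a simpler alternative, but it drops those without a 3-month value.

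If results are already known, keep the planned analysis as primary and report this beside it, labelled as supplementary.

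The cost is one further model per outcome in software already used, with no new data. There is also a reporting cost. The model gives a single baseline mean, so arm-specific baseline means must come from raw summaries, and model-based within-group changes are measured from the common baseline.

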## Participants

### Eligibility

To be eligible, participants must be female and meet the following inclusion criteria: (1) currently 55 years or older; (2) sit for more than 7 hours on a majority of device-measured days, as assessed by activPAL (as given in the *Screening Visit* section); (3) do 70 or fewer sit-to-stand transitions on a majority of device-measured days, as assessed by activPAL; (4) no health conditions that would inhibit standing; (5) able to read and write fluently in English; (6) postmenopausal, defined as no menstrual period in the last 12 months; (7) BMI $\geq$ 25 kg/m^2 and <45 kg/m^2; (8) able to walk, stand, and perform sit-to-stand transitions without a high risk of falling, determined by the Short Physical Performance Battery (SPPB); and (9) able to travel to study visits. Exclusion criteria include (1) the use of insulin, (2) uncontrolled diabetes defined as HbA1c>10%, (3) uncontrolled blood pressure defined as systolic blood pressure>180 or diastolic blood pressure>110, and (4) participation in another research study or program that would impact the outcomes of this study.

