During the first 60-minute in-person session, the health coach provides an overview of the intervention and gives participants a binder of printed educational materials and safety tips, printed action plan forms, and tracking logs. First, participants are asked to share their motivation to join the study. Next, they review reasons for sitting, dangers of prolonged sitting, and benefits of breaking up sitting. Tips for safely reducing sitting or increasing sit-to-stand transitions based on group assignments are reviewed. The health coach models the target behavior by having participants in the Reduce Sitting arm practice standing for up to 5 minutes in the middle of the session, and participants in the Increase Transitions arm perform 3 brief sit-to-stand transitions in a row, holding each for 5 seconds, twice during the session. Participants are then given a wrist-worn activity band that is programmed to prompt sitting breaks based on group assignment (refer to the *Toolbox* section). Participants are shown graphs from activPAL data, either of time spent sitting or sit-to-stand transitions, depending on the group assignment (Figures 1 and 2). The health coach and participants use the graphs to (1) review a typical day and identify times during the day when participants may be able to take sitting breaks or perform sit-to-stand transitions, (2) set behavior change goals for the next week, and (3) create a specific action plan. Participants complete an action plan by identifying the specific strategy, location, days of the week, time of day, and tailored goals for the participant (number of minutes to reduce sitting by or number of transitions to complete). Participants brainstorm potential obstacles to following the action plan and solutions for overcoming each obstacle. Using motivational interviewing techniques, confidence is assessed and supported using a 0 (very low confidence) to 10 (very high confidence) scale (*ruler*). To further support behavior change, participants are provided with several tools they can choose to use. As people vary in their preferences and needs, a toolbox approach allows participants to select tools they want to try (refer to the *Toolbox* section). At the end of the session, participants are given an activPAL to wear for the next 7 days and bring in the following week so that they can review their behavior with their health coach. If the participant provides consent, the health coach sessions are audio recorded for quality checks and training.

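### The random-intercept model gives both visits and each fitted arm one common variance, so the reported 95% CIs for visit means and within-group changes can miss their stated level, chiefly for sitting and transitions; the primary contrast is essentially unaffected in pairwise fits.

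*SAP*

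**What the plan says.** The SAP (Statistical Plan, primary analysis) fits baseline and 3-month values jointly as the dependent variable. Its fixed part is given as "time (baseline, 3-month), group (active, control), and the group*time interaction were fixed-effect independent (categorical) variables". Its only random term is described thus: "A subject-specific (random) intercept was included to model individual heterogeneity in outcomes". The software statement is "LMMs were executed by R package nlme"; no variance function, unstructured covariance or robust standard error is named. The one safeguard is that "diagnostic plots were generated to evaluate model assumptions", with no action attached.

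On reporting, the SAP lists the visit means first: "For the other outcomes, sedentary behavior measures, and blood pressure, mean (95% CI) at baseline and 3 months". Changes over time within each arm are to be reported from the same fit: "as well as mean (95% CI) within-group change derived from model parameters". These intervals therefore come from the model, and they cover the behaviors that the interventions target.

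Two features of the Protocol bear on the variances. Under Eligibility, women must sit for more than 7 hours, and must "do 70 or fewer sit-to-stand transitions on a majority of device-measured days, as assessed by activPAL". Under Health Coaching Sessions, the action plan in both intervention arms contains "tailored goals for the participant (number of minutes to reduce sitting by or number of transitions to complete").

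**The concern.** With two visits, a random intercept plus one residual variance leaves two covariance parameters for all arms in the fit. Total variance is then the same at both visits, and the variance of change is the same in each arm. The design gives two separate reasons to doubt this for sitting and transitions.

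- **Selection at entry.** Cutting on baseline sitting and transitions narrows baseline spread, and some of that spread should return at 3 months. The cut applies to every arm alike, so it sets visit against visit, not arm against arm.
- **Tailored coaching.** Women in a coached arm set their own goals and choose their own tools, so their responses may vary more than those of controls, who work on other topics. This sets arm against arm.

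The within-group changes in sitting and transitions are what a reader uses to judge whether each arm changed its target behavior. If the SDs of change differ, precision is overstated in the coached arm and understated in control.

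**Working it through.** **Inputs.** From the SAP: the random-intercept model, the 95% intervals and the two-level group coding. From the Protocol (Study Objectives): 405 women in 3 arms; 135 per arm assumes equal allocation (405/3), but n cancels from every ratio below. The documents give no SD or correlation for any outcome, so all SD ratios are assumptions.

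**Formulas (complete data, equal arms).** The model's SE of a within-arm change is sqrt(mean of the arms' change variances / n). The true SE is sqrt(that arm's change variance / n). With R = model SE / true SE, coverage = 2Φ(1.96R) − 1.

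**Stated figure.** With equal SDs R = 1 and coverage is 95%, so the nominal level is reproduced. A REML simulation with equal variances gave 94–96%.

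**Within-group change, two-arm fit.** Set the control SD of change to 1 and the coached SD to k. The pooled variance is (1 + k²)/2. For the coached arm R = sqrt((1 + k²)/2)/k; the control CI is too wide by the factor sqrt((1 + k²)/2).

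| k | Pooled variance | R, coached | Coverage, coached | Control CI width factor |
|---|---|---|---|---|
| 1.0 | 1.000 | 1.000 | 95.0% | 1.00 |
| 1.1 | 1.105 | 0.956 | 93.9% | 1.05 |
| 1.25 | 1.281 | 0.906 | 92.4% | 1.13 |
| 1.5 | 1.625 | 0.850 | 90.4% | 1.27 |
| 2.0 | 2.500 | 0.791 | 87.9% | 1.58 |
| 2.5 | 3.625 | 0.762 | 86.5% | 1.90 |

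**Visit means, spread wider at 3 months in all arms.** Let the 3-month SD be m times baseline in every arm. The model SE uses the average variance (1 + m²)/2 at both visits. At m = 1.25 the 3-month CI covers 92.4% and the baseline CI 97.3%; at m = 1.5, 90.4% and 98.8%. The change CIs stay at 95%, because the arms do not differ.

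**Primary contrast, two-arm fit.** The model variance of the difference in changes is 2 × (1 + k²)/2 / n = (1 + k²)/n, which equals the true variance. R = 1 for every k, so coverage is 95%.

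**Joint three-arm fit, if one were used.** Assume Reduce Sitting at 1.1 and Increase Transitions at k, so that the pooled variance is (1 + 1.21 + k²)/3.

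- k = 1.5: pooled 4.46/3 = 1.487. The Reduce Sitting versus control SE is too large by sqrt(2 × 1.487/2.21) = 1.16. Increase Transitions versus control has R = sqrt(2 × 1.487/3.25) = 0.956, coverage 93.9%.
- k = 2.5: pooled 8.46/3 = 2.82. The factors are sqrt(5.64/2.21) = 1.60 and sqrt(5.64/7.25) = 0.882, the latter giving coverage 91.6%.

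**Incomplete records.** Where 3-month values are missing, the equal-variance assumption also sets how much the baseline value counts in their place. In a simulation assuming 15% missing depending on baseline and a 3-month SD 1.5 times larger in one arm, that arm's estimated change was biased by about 0.04 baseline SD.

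**The case against.** The strongest reply is that the trial's conclusion rests on the group-by-time contrast for the two composites. The group coding (active, control) reads most naturally as separate active-versus-control fits, and there the contrast's SE is right. This stands. A reader might infer from the model's form that the primary tests are invalid; the documents do not support that. The three-arm figures apply only to a joint fit, which the SAP does not describe.

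Second, nothing in the documents shows that the arms' SDs differ, and mild differences cost little: about one point of coverage at a ratio of 1.1. This also stands, so the range must start at no error. A reader might take the eligibility cut as evidence that the change CIs are wrong; it is not, since it is common to all arms and touches only visit means. Nor does anything show arm-specific widening for the biomarkers or blood pressure, and insulin, glucose and HOMA2-IR are log-transformed.

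Third, nlme can fit unequal variances, and the SAP promises diagnostics. The SAP is silent rather than exclusionary, so stating that such a structure was used would close the point. But silence leaves the described model as the plan, and diagnostic plots with no consequence attached do not protect the intervals.

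**Conclusion.** The point holds as a conditional one. As described, the model imposes equal variances across visits and fitted arms, and the reported CIs for visit means and within-group changes inherit that assumption. The design makes it doubtful for sitting and transitions, though the documents cannot show by how much. In a two-arm fit the coached arm's change CI covers about 94%, 92%, 90%, 88% or 86% at assumed SD ratios of 1.1, 1.25, 1.5, 2 or 2.5, and the control CI is 1.05 to 1.9 times too wide; at a ratio of 1 nothing is wrong.

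With near-equal arms, complete data and pairwise fits, the primary contrast is not materially affected. Between-arm SEs would be off only in a joint three-arm fit: at ratios of 1.5 to 2.5, Reduce Sitting versus control 1.16 to 1.6 times too large, and Increase Transitions versus control covering 92–94%. This is a correction to reported intervals, worth making because it is cheap; it is not a flaw in the primary test.

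**What to change.** For the two visits, use an unstructured covariance estimated separately by arm, with both visit variances and the correlation arm-specific. Because the primary model is saturated in arm and visit, this can be done in nlme by fitting the two-visit covariance within each arm and combining the arms' independent estimates for the treatment effect. Take every visit-mean, within-group-change and treatment-effect CI from that fit, at minimum for the sedentary behavior measures.

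Freeing the variances by arm and visit while sharing one correlation is not enough. If the extra change variance is independent of baseline (assumed control SD of change 10, baseline SD 10–15, ratios 1.5–2.5), the control change CI in a two-arm fit is still about 5–18% too wide.

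A simpler alternative for the CIs is to keep the model and use cluster-robust SEs by participant; this leaves the point estimates, and their handling of missing 3-month values, as they are. The SAP should also say whether the arms are fitted in pairs or jointly.

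The cost is one or two SAP sentences, a few lines of code, and a rerun if results already exist. A two-arm fit has 2 × 3 = 6 covariance parameters instead of 2, which is negligible with about 135 women per arm (assuming equal allocation of 405).

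### The randomisation strata are left out of the primary mixed model, and the stratum-adjusted secondary analysis does not state its form; as main effects only it would be a weak check on the group*time result

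*SAP*

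**What the plan says.** The Protocol (Baseline Visit) names two stratification factors: "Randomization is stratified by BMI (overweight vs obese) and employment status (full-time vs nonfull-time employment". It adds: "A stratified permuted block design is used in this study". Block size is not given.

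The SAP lists the fixed effects of the primary model as "time (baseline, 3-month), group (active, control), and the group*time interaction were fixed-effect independent (categorical) variables", with a random intercept per woman. Baseline and 3-month values are both outcomes, and "this difference of outcome changes between intervention and control arms represents the intervention effect". Women with only one of the two measurements stay in the model, which is described as "allowing for the inclusion of partially complete records".

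The strata enter only the first of the secondary analyses: "First, we evaluated intervention effects adjusted for baseline stratification variables (obesity status, employment status". The SAP does not say whether they are added as main effects or also crossed with time.

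**The concern.** An analysis normally carries the factors used to restrict the randomisation. Blocking balances the strata across arms, so the treatment comparison already benefits from them. A model without them still counts any stratum difference in change as error, so its standard error can be a little too large.

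The secondary analysis looks like the remedy, but whether it is one depends on its form. In a model for both time points, a baseline factor entered as a main effect explains differences in level, while the effect tested is a difference in change. If only main effects were used, agreement between the adjusted and primary results is close to guaranteed and says little about robustness. At stake are a little precision and the meaning of a robustness check, not the validity of the primary test.

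**Working it through.** **1. Where the strata drop out.** Write the outcome of woman *i* at time *t* (0 or 1) as arm and time terms + γS + δS·t + random intercept + error, where S is a stratum indicator. With both times observed, group*time is estimated from the change Y1 − Y0. There γS cancels and δS remains. So main effects cannot alter group*time for complete pairs; stratum*time terms can.

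**2. Complete-data precision.** From the documents: 405 women in three arms and two-sided alpha 0.025 per comparison (critical value 2.2414). The documents give no stratum frequencies, correlation or gap in change. Assumed: 50% obese, 35% full-time, the two factors independent, baseline-to-3-month correlation r of 0.5 or 0.7, and gaps in change expressed in baseline SDs.

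- Variance of change within strata: 2(1 − r), which is 1.0 or 0.6.
- Added by the strata with the same gap in both factors: gap² × (0.5×0.5 + 0.35×0.65) = gap² × 0.4775.
- SE ratio, with stratum*time against without: √[2(1 − r) / (2(1 − r) + gap² × 0.4775)].
- Actual alpha of the model without strata: 2 × [1 − Φ(2.2414 / ratio)].
- Equivalent women: 405 × (1/ratio² − 1).

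| Gap in both factors | r | SE ratio | SE cut | Variance of change explained | Alpha without strata | Women |
|---|---|---|---|---|---|---|
| 0 | 0.5 or 0.7 | 1 | 0% | 0% | 0.0250 | 0 |
| 0.15 SD | 0.5 | 0.9947 | 0.5% | 1.1% | 0.0242 | 4 |
| 0.15 SD | 0.7 | 0.9912 | 0.9% | 1.8% | 0.0237 | 7 |
| 0.3 SD | 0.5 | 0.9792 | 2.1% | 4.1% | 0.0221 | 17 |
| 0.3 SD | 0.7 | 0.9660 | 3.4% | 6.7% | 0.0203 | 29 |

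With a 0.3 SD gap in one factor only:
- Obesity: √(1/1.0225) = 0.989 and √(0.6/0.6225) = 0.982.
- Employment: √(1/1.0205) = 0.990 and √(0.6/0.6205) = 0.983.
- The cut is therefore 1.0-1.8%.

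**3. A worked fit.** One simulated three-arm data set of 405 women (135 per arm, no blocking, intercept SD 0.8, residual SD 0.55, obesity effect 0.6 on level and 0.3 on change) was fitted three ways by REML. Entries are the two group*time estimates, with standard errors in brackets.

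| Data | No strata | Main effects | Stratum*time |
|---|---|---|---|
| Complete | 0.10396, 0.01595 (0.0982) | 0.10396, 0.01595 (0.0982) | 0.10229, 0.01235 (0.0968) |
| 15% missing at 3 months | 0.04348, −0.01937 (0.1081, 0.1072) | 0.04493, −0.01136 (0.1081, 0.1071) | 0.04693, −0.00800 (0.1065, 0.1056) |

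With complete pairs, main effects change nothing. With missing values they move the second estimate by 0.0080, or 0.0080/0.1072 = 0.07 SE, and leave the SE almost where it was. Only the crossed terms lower it.

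**4. Partial records more generally.** In repeated simulation, 10% or 20% of 3-month values were missing, either completely at random or twice as often in full-time women equally in all arms. Assumed level effects were 0 to 0.6 SD, gaps in change 0 to 0.3 SD, and blocks of 6. Main effects gave a mean SE ratio of 0.994-1.0004 and an RMS shift in the estimate of 0.001-0.018 SD, about 0.01-0.13 SE. The largest shift in any single trial was 0.065 SD. Mean estimates stayed within 0.01 SD of the true null in every model.

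**The case against.** The other side has four arguments.

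- **The SAP does plan a stratum-adjusted analysis, and nothing is invalid.** This stands. A reader might infer that omitting the strata biases the primary test or raises its false-positive rate. The calculation shows the opposite direction: alpha stays at or below 0.025.

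- **The form can largely be read from context.** The SAP spells out interactions elsewhere: it "evaluated 3-way COVID-19*group*time interaction (by likelihood ratio tests", and it names an MVPA-by-group term. Asking "whether baseline hypertension status was an effect modifier for blood pressure" implies an interaction by definition. Plain adjustment would then ordinarily mean added main effects. This mostly stands, so it would be too strong to say the form cannot be inferred at all. But that reading is the one under which the analysis is a weak check, so it sharpens the point.

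- **Main effects are not inert.** A reader might infer that crossing with time alone decides whether the adjusted result can differ from the primary one. That holds only when every woman has both measurements. The SAP keeps partial records, so main effects can move the estimate, usually by a small fraction of an SE.

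- **The gain is hypothetical.** Only the 405 and the alpha come from the documents. The upper end needs a 0.3 SD gap in change for obesity and employment together, which nothing in the documents supports. This stands too, and it is why the range starts at zero.

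**Conclusion.** The point holds and is minor. The strata used in the randomisation are absent from the primary model, and the one analysis that uses them does not state its form. If it used main effects only, it reproduces the primary result exactly for complete pairs and usually nearly so with modest missingness, so agreement would be weak evidence of robustness.

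The primary test is at most slightly conservative, and only if obesity or employment predicts 3-month change. The possible gain in standard error runs from 0% to 3.4%. It rests on assumed stratum frequencies, correlations and gaps in change; none is given in the documents. The conclusion about main effects with partial records rests on assumed missingness of 10-20%.

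**What to change.** Fit the stratum-adjusted mixed model for both composites and for the individual markers with obesity status, employment status, obesity*time and employment*time. State those terms in the SAP and report the result beside the primary one. The SAP is written in the past tense, so this is the practical route.

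If the primary model is in fact not locked, make this the primary model and keep the model without strata as a sensitivity analysis. Otherwise label any change to the primary model post hoc.

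The cost is one sentence in the SAP and four fixed-effect terms, in variables known for every woman at randomisation. In the simulations with strata that did not predict change, the mean SE ratio was 1.000 with complete data and at most 1.0007 with 10-20% missing, so essentially no precision is lost.
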